10.3 SAFETY ANALYSIS

All safety analyses will be performed on the safety set.

10.3.1 Adverse events

Unless otherwise specified, the analyses of adverse events (AEs) will be descriptive in nature. All analyses of AEs will be based on the number of patients with AEs and NOT on the number of AEs.

All AEs occurring between the initiation of JARDIANCE® Tablets prescribed at baseline visit and 7 days (inclusive) after the last administration will be considered ‘treatment emergent’.

Furthermore, for analysis of AE attributes such as duration, severity, etc. multiple AE occurrence data on the CRF will be collapsed into AE episodes provided that all of the following applies:

- The same MedDRA lowest level term was reported for the occurrences.
- The occurrences were time-overlapping or time-adjacent (time-adjacency of 2 occurrences is given if the second occurrence started on the same day or on the day after the end of the first occurrence).
- Treatment did not change between the onset of the occurrences OR treatment changed between the onset of the occurrences, but no deterioration was observed for the later occurrence.

For further details on summarization of AE data, please refer to BI standards (‘Analysis and Presentation of Adverse Event Data from Clinical Trials’ [\(2\)](#)).

Unless otherwise specified, AE analyses will be used AE data from safety database.

An Adverse Drug reaction (ADR) is defined as an AE for which either the investigator or the sponsor (or both) assesses the causal relationship to JARDIANCE® as “Yes.” A serious AE is defined as an AE for which either the investigator or the sponsor (or both) assesses the seriousness as “Serious.”

The SOCs will be sorted according to the standard sort order specified by European medicines agency. PTs will be sorted by frequency (within SOC).

The frequency of patients with the following items will be summarized.

- AEs
- ADRs
- Severe AEs
- Severe ADRs (Dr)
- AEs leading to discontinuation
- ADRs (Dr) leading to discontinuation
- AEs leading to all-cause death
- ADRs leading to all-cause death
- AEs leading to CV death
- ADRs leading to CV death
- AEs leading to hospitalization for HF
- ADRs leading to hospitalization for HF
- Serious AEs
- Serious ADRs

Note1: Severe AEs/ADRs and AEs/ADRs leading to discontinuation will be used AE data from CRF.

Note2: For the definition of all-cause death, CV death and HF, refer to note in Section [10.2.5](#).

Note3: ADRs (Dr) is defined as an AE for which only the investigator assesses the causal relationship to JARDIANCE® as “Yes”.

The frequency of patients with the following items will be summarized by primary SOC and PT.

- AEs
- ADRs
- AEs leading to discontinuation
- ADRs (Dr) leading to discontinuation
- AEs leading to all-cause death
- ADRs leading to all-cause death
- AEs leading to CV death
- ADRs leading to CV death
- AEs leading to hospitalization for HF
- ADRs leading to hospitalization for HF
- Serious AEs
- Serious ADRs

Note1: AEs/ADRs leading to discontinuation will be used AE data from CRF.

Note2: For the definition of all-cause death, CV death and HF, refer to note in Section [10.2.5](#).

Note3: ADRs (Dr) is defined as an AE for which only the investigator assesses the causal relationship to JARDIANCE® as “Yes”.

[figure not shown]
The listings in the following items are presented.

- AEs leading to discontinuation used AE data from CRF.

- AEs obtained from the safety database with different assessments of the causal relationship to JARDIANCE® judged by between the sponsor and the investigator.

Summaries for the time to onset of first episode for the ADRs will be tabulated, by duration (0 to <12, 12 to <26, 26 to <40, 40 to <52, ≥ 52 , Unknown [weeks]), by primary SOC, and PT.

To compare risks of overall ADR in different patient subgroups, frequency tabulation stratified by the subgroups will be provided with odds ratios for the incidence of ADR and 95% confidence intervals for the odds ratios whenever specified (see [Table 10.3.1: 1](#)). The odds ratio and the 95% confidence intervals for the odds ratios will be calculated by use of Logistic regression. In case that there will be a significant difference between each factor in the subgroups (i. e. in the case that the confidence interval for the odds ratio will not include the number 1), the frequency of patients with ADR will be summarized by the factor, primary SOC and PT.

[figure not shown]

[figure not shown]
BOEHRINGER INGELHEIM Group of Companies

[figure not shown]
1245-0286

[figure not shown]
Page 21 of 26

c44536556-01

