7.2.1 Primary outcomes

The primary endpoint of this study is the incidence of ADRs (focus on hypoglycaemia, the events relevant volume depletion, influence of ketone body increased / ketoacidosis and renal impairment).

There is no primary outcome for effectiveness as the primary objective of a PMS is evaluating safety.

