10.1 MAIN ANALYSIS

[figure not shown]
The analysis of the primary outcomes is described in [Section 10.3.1](#).

[figure not shown]
In this PMS, since the primary endpoint is the incidence of ADRs (focus on hypoglycaemia, the events relevant volume depletion, influence of ketone body increased / ketoacidosis and renal impairment), the main analysis is to show frequency, proportion and its corresponding confidence interval (CI). The details are given in [Section 10.3.1](#).

[figure not shown]

[figure not shown]

[figure not shown]

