10.3.2 Endpoints related to safety

For safety set, duration of treatment exposure adjusted incidence rate, frequency, proportion and its corresponding confidence interval (CI) in all-cause death, incidence of CV death, incidence of initial hospitalizations for HF and Safety specifications will be shown in the same way as [Table 10.2.5: 1](#).

Kaplan-Meier analysis will be used to estimate incidence of all-cause death, incidence of CV death, incidence of initial hospitalizations for HF rate and incidence of CV death or initial hospitalizations for HF and a Kaplan-Meier plot and Safety specifications will be constructed.

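### The ADR table by subgroup factor, SOC and PT depends on a significant overall-ADR odds ratio, so a subgroup difference confined to one focus ADR group may go unshown

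*SAP*

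**What the plan says.** Section 7.2.1 of the SAP defines the primary endpoint as the incidence of ADRs, with a "focus on hypoglycaemia, the events relevant volume depletion, influence of ketone body increased / ketoacidosis and renal impairment". Section 10.3.1 starts from the position that AE analyses are descriptive unless otherwise specified.

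The subgroup analysis later in Section 10.3.1 has two steps.

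- Step one is unconditional. Its purpose is "To compare risks of overall ADR in different patient subgroups", by frequencies and odds ratios for the factors in Table 10.3.1: 1. On method: "The odds ratio and the 95% confidence intervals for the odds ratios will be calculated by use of Logistic regression".
- Step two is conditional. Where a factor shows a significant difference, explained as "in the case that the confidence interval for the odds ratio will not include the number 1", then "the frequency of patients with ADR will be summarized by the factor, primary SOC and PT".

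The readable text gives no other route to the step-two table. Section 10.3.2 adds that "Safety specifications will be shown in the same way as" Table 10.2.5: 1. That table is not shown, and the readable sentence covers the safety set without mentioning subgroups.

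**The concern.** The condition tests one quantity and the table it controls shows another. The odds ratio pools every ADR, while the table would show which kind of ADR differs. If a factor changes the risk of one focus group and leaves the rest alone, the other ADRs add equally to both subgroups and pull the overall odds ratio towards 1. If the factor raises one kind of ADR and lowers another, the two offset each other. In both situations the detailed table is most likely to be withheld when it would be informative.

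The condition can also be met by chance. It is applied factor by factor at the 5% level and no adjustment is stated, so which factors receive a detailed table depends partly on luck.

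What is at stake is limited to this one output: which SOC or PT, possibly a focus ADR, differs between subgroups. The whole-set estimates of Section 10.1, the overall SOC and PT tables, and the overall-ADR subgroup frequencies and odds ratios do not depend on the condition.

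**Working it through.** **Inputs.** From the SAP: the 95% confidence level, logistic regression, any ADR as the outcome, and the rule that the interval must exclude 1. The readable text has no sample size, ADR rates, subgroup shares or factor count, so there is no stated figure to reproduce. Everything below is assumed and varied.

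**Set-up.** There is one binary factor, unadjusted. One focus ADR has risk f0 or f1 in the two subgroups, and all other ADRs have risk o, equal in both unless stated. The overall ADR risk is o + f if no patient has both kinds (no overlap), or 1 − (1 − o)(1 − f) if they are independent. In each range of two percentages below, the first is for independence and the second for no overlap.

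**Method.** Exact binomial enumeration over both subgroups of how often the Wald 95% CI of the log odds ratio excludes 0, with SE = √(1/a + 1/b + 1/c + 1/d), where a to d are the four cell counts. Outcomes with a zero cell count as not excluding.

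**One case by hand.** N = 1000, 500 per subgroup, o = 9%, focus 1% v 3%, no overlap:

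- Overall risks are 10% and 12%. The odds ratio is (0.12/0.88)/(0.10/0.90) = 1.23, with log 0.205.
- SE = √(1/60 + 1/440 + 1/50 + 1/450) = 0.203, so the expected z is about 1.01.
- The chance of passing 1.96 is about Φ(1.01 − 1.96) = Φ(−0.95) ≈ 17%. Enumeration gives 17.0%, and 15.0% under independence.
- For the focus ADR alone, the odds ratio is (0.03/0.97)/(0.01/0.99) = 3.06. Its interval would exclude 1 in 59.3% by enumeration.

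**Results by enumeration.**

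| N | Split | Other ADRs | Focus ADR | Condition met | CI on focus ADR itself excludes 1 |
|---|---|---|---|---|---|
| 500 | 50/50 | 9% | 1% v 3% | 9.7–10.7% | 19.0% |
| 1000 | 50/50 | 9% | 1% v 3% | 15.0–17.0% | 59.3% |
| 2000 | 50/50 | 9% | 1% v 3% | 25.7–29.7% | 90.3% |
| 1000 | 50/50 | 4% | 1% v 3% | 24.6–26.1% | 59.3% |
| 1000 | 50/50 | 14% | 1% v 3% | 11.5–13.8% | 59.3% |
| 1000 | 80/20, higher risk in the 20% | 9% | 1% v 3% | 12.6–14.0% | 52.6% |
| 1000 | 50/50 | 9% | 1% v 2% | 7.4–7.9% | 20.0% |
| 500 | 50/50 | 9% | 1% v 2% | 6.1–6.3% | 3.8% |
| 1000 | 50/50 | 4% | 2% v 6% | 61.5–64.3% | 90.8% |
| 1000 | 50/50 | 4% | 3% v 9% | 87.0–88.9% | 98.4% |
| 1000 | 50/50 | 9% | 2% v 6% | 40.9–46.8% | 90.8% |
| 1000 | 50/50 | 9% | 3% v 9% | 69.1–75.9% | 98.4% |

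The table is absent in 1 minus the condition-met column. The last column only measures dilution; neither the SAP nor the proposed change tests the focus ADR. In the 1% v 2% case at N = 500, neither interval is informative.

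**Opposite differences.** With focus 1% v 3% and other ADRs 9% v 7%, the overall risk is 10% in both subgroups without overlap (1% + 9% and 3% + 7%) and 9.9% v 9.8% under independence. The condition is met in about 5% at N = 500, 1000 and 2000. A larger study does not help.

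**Chance openings.** With k independent factors and no true difference, the chance that at least one meets the condition is 1 − 0.95^k: 23% for k = 5, 40% for k = 10 and 64% for k = 20.

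**The case against.** The strongest objection is that parts of the SAP cannot be read. Section 10.2 and Tables 10.2.5: 1 and 10.3.1: 1 are not shown, and a breakdown of the focus groups by subgroup might be there. This stands as a limit on the consequence. It does not alter the condition itself, which is fully readable.

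Second, the rule is fixed in advance, contradicts nothing, and drills down only where the overall comparison differs. The SAP sets no objective to find which SOC or PT varies by subgroup. It also says the table follows if the condition holds, without forbidding it otherwise. That is fair, but a significance screen on any ADR suits a descriptive safety analysis focused on four specific groups poorly, and no other route to the table is stated.

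Third, SOC and PT rows are not focus groups. At N = 1000 with equal subgroups, 1% v 3% means about 5 v 15 patients, who may be spread over several PTs. Removing the condition alone might not make the pattern visible. This is correct, and is why the fix also asks for a focus-group tabulation.

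Fourth, all magnitudes are assumed, and the opposite-direction case was built so that the overall rates match. Both points are true; the figures show how the rule behaves and do not forecast this study.

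Last, a chance opening only adds one descriptive table, while the fix prints them all and so displays more chance differences. That stands as the cost of the change.

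**Conclusion.** The concern holds. The SAP makes a descriptive safety table depend on a significance test of a broader outcome than the ones the study is focused on. The condition is less sensitive to a focus-group difference, though not blind to it. For a rare focus ADR (1% v 3%, other ADRs 9%, equal subgroups) the table would be absent in about 89–90% of cases at N = 500, 83–85% at N = 1000 and 70–74% at N = 2000. When the focus ADR is a large share of all ADRs it is usually produced: at N = 1000 with other ADRs 4%, it is absent in about 36–39% (2% v 6%) and 11–13% (3% v 9%).

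These sizes rest on the assumed sample size, rates, split and overlap, and on an unadjusted model with a binary factor. The consequence also depends on the unseen parts of the SAP not already giving the breakdown. No primary estimate is biased and no data are lost. This is a reporting weakness that should be corrected, because correcting it is cheap.

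**What to change.** In Section 10.3.1:

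- Delete the condition on the confidence interval and produce the descriptive ADR table by factor, primary SOC and PT for every factor in Table 10.3.1: 1.
- Tabulate the four focus ADR groups by the same factors, unless Section 10.2 or the tables not shown already do so.
- Keep the overall-ADR odds ratios, and label all subgroup comparisons exploratory and unadjusted for multiplicity.

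This needs no new data, model or test, only extra tables from data already collected. The downside is a longer appendix with more chance differences on display, which the exploratory label flags but does not remove.

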10.3.2 Endpoints related to safety

For safety set, duration of treatment exposure adjusted incidence rate, frequency, proportion and its corresponding confidence interval (CI) in all-cause death, incidence of CV death, incidence of initial hospitalizations for HF and Safety specifications will be shown in the same way as [Table 10.2.5: 1](#).

Kaplan-Meier analysis will be used to estimate incidence of all-cause death, incidence of CV death, incidence of initial hospitalizations for HF rate and incidence of CV death or initial hospitalizations for HF and a Kaplan-Meier plot and Safety specifications will be constructed.

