7.2.2 Secondary outcomes

- Incidence of all-cause death
- Incidence of CV death
- Incidence of hospitalizations for heart failure

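### Kaplan-Meier incidence of CV death, first HF hospitalization and their composite runs slightly high in Section 10.3.2, unless Section 10.2.5 handles competing deaths

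*SAP*

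**What the plan says.** SAP Section 7.2.2 lists three secondary outcomes: "Incidence of all-cause death", "Incidence of CV death" and "Incidence of hospitalizations for heart failure". Section 10.3.2 plans two kinds of summary for them.

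- The first sentence plans an exposure-adjusted rate together with "frequency, proportion and its corresponding confidence interval (CI) in all-cause death, incidence of CV death, incidence of initial hospitalizations for HF", laid out like Table 10.2.5: 1.
- The second sentence reads "Kaplan-Meier analysis will be used to estimate incidence of all-cause death, incidence of CV death, incidence of initial hospitalizations for HF rate" and goes on to "incidence of CV death or initial hospitalizations for HF and a Kaplan-Meier plot and Safety specifications will be constructed".

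The composite of CV death or first HF hospitalization is listed only in the second sentence.

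Section 10.3.1 handles definitions by reference: "For the definition of all-cause death, CV death and HF, refer to note in Section" 10.2.5. That section and its table are not in the public text. The Kaplan-Meier sentence itself does not refer to Section 10.2.5. The visible text mentions neither competing risks nor a cumulative incidence function, and it does not say how other deaths enter these curves.

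**The concern.** One estimator is named for four endpoints, and as an estimator of incidence it fits only one of them. All-cause death has no competing event. Non-CV death rules out a later CV death, and it rules out the composite in a patient who has not yet had it. Any death before a first HF hospitalization rules that hospitalization out.

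If these deaths are censored, Kaplan-Meier treats the dead patients as though they could still have the event, at the same rate as those still followed. The result estimates the risk in a setting where nobody dies of the competing cause. A reader of a 52-week figure labelled incidence will take it as the share of treated patients who had the event.

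Two of the three secondary outcomes are affected. For these two, the crude proportion in the first sentence of Section 10.3.2 does not carry this bias. For the composite, that section offers no such figure alongside.

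**Working it through.** **Inputs.** The SAP gives up to 52 weeks of follow-up (Section 7.1) and day 364 as the planned day for week 52 (Table 6.4: 1). It gives no event rate and no number of patients, so there is no planned figure to reproduce. All hazards below are assumptions (constant, per year). The 500 to 1500 patients used for precision are also assumed.

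**Formulas.** With event hazard h1, competing-death hazard h2 and t = 364/365.25 = 0.9966 years:

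- 1-KM, competing deaths censored: 1 − exp(−h1·t)
- Cumulative incidence (CIF): h1/(h1+h2) × [1 − exp(−(h1+h2)·t)]
- Excess: 1-KM minus CIF; relative excess: excess divided by CIF

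**Worked case, first HF hospitalization (h1 = 0.10, h2 = 0.08).**

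- 1-KM = 1 − exp(−0.09966) = 9.49%.
- CIF = 0.10/0.18 × [1 − exp(−0.17938)] = 0.5556 × 0.1642 = 9.12%.
- Excess = 0.36 points, or 4.0% relative.

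**Low, central and high assumptions.**

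| Endpoint (competing event) | h1, h2 | 1-KM | CIF | Excess, points | Relative |
|---|---|---|---|---|---|
| CV death (non-CV death) | 0.02, 0.01 | 1.97% | 1.96% | 0.01 | 0.5% |
| | 0.05, 0.03 | 4.86% | 4.79% | 0.07 | 1.5% |
| | 0.15, 0.10 | 13.89% | 13.23% | 0.65 | 4.9% |
| Composite (non-CV death) | 0.07, 0.01 | 6.74% | 6.71% | 0.03 | 0.5% |
| | 0.15, 0.03 | 13.89% | 13.69% | 0.20 | 1.5% |
| | 0.45, 0.10 | 36.14% | 34.52% | 1.6 | 4.7% |
| First HF hospitalization (any prior death) | 0.05, 0.03 | 4.86% | 4.79% | 0.07 | 1.5% |
| | 0.10, 0.08 | 9.49% | 9.12% | 0.36 | 4.0% |
| | 0.30, 0.25 | 25.84% | 23.02% | 2.8 | 12.3% |

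In each scenario the HF hospitalization row takes the sum of the CV and non-CV death hazards as its competing hazard. For all-cause death h2 = 0, so the two formulas coincide and the excess is zero.

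**Against sampling error.** The half-width is 1.96 × √[CIF(1 − CIF)/n], at n = 500 and n = 1500, for the central cases.

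| Endpoint | Half-width, points | Excess / half-width |
|---|---|---|
| CV death | 1.87 and 1.08 | 0.04 and 0.07 |
| Composite | 3.01 and 1.74 | 0.07 and 0.12 |
| First HF hospitalization | 2.52 and 1.46 | 0.14 and 0.25 |

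In the high HF hospitalization case the ratio is 0.77 and 1.33.

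**When it stops being slight.** Setting the HF hospitalization excess to 1 point and solving for h2 gives 0.232, 0.156 and 0.084 at h1 = 0.10, 0.15 and 0.30. Through 1 − exp(−h2·t), these are 52-week death risks of 20.6%, 14.4% and 8.0%.

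**Simulation check.** With 4 million simulated patients under the central hazards, the excess was 0.071 points for CV death, 0.199 for the composite and 0.363 for HF hospitalization, in line with the formulas.

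**The case against.** The strongest objection is that the public text lacks Section 10.2.5, to which the SAP sends the definitions of these endpoints. Competing deaths may be dealt with there, and text that is withheld is not an omission. This stands as a condition on the point. It does not remove it, because Section 10.3.2 positively names Kaplan-Meier as the estimator, and that sentence does not defer to Section 10.2.5.

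The second objection is that the effect hardly matters: one cohort, descriptive secondary outcomes, an excess well inside sampling error in the central cases, and crude proportions for two of the three endpoints. This stands too, and it is why the point is only an optional improvement. It does not help the composite, which has no crude proportion in Section 10.3.2.

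Third, the HF hospitalization figures use the total death hazard as the hazard of death before a first hospitalization. If deaths cluster after hospitalization, the competing hazard is lower and the excess smaller. For example, halving h2 to 0.04 in the central case gives a CIF of 9.30% and an excess of 0.18 points. The same caution applies to the death-risk thresholds.

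Fourth, only the competing-death component has a known sign. If follow-up in these curves ends when treatment stops, informative censoring could move the estimate in either direction. That is a separate issue and does not undo this one.

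Finally, Kaplan-Meier with competing deaths censored can be defended as describing a cause-specific quantity. The SAP, however, calls the target incidence, and for incidence the cumulative incidence is the matching estimate.

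**Conclusion.** The point holds as a minor, conditional one. Unless Section 10.2.5 handles competing deaths, the Kaplan-Meier incidence of CV death, first HF hospitalization and their composite overstates the share of patients with the event by week 52. The direction of this component is a mathematical property. Its size rests on assumed constant hazards: over the ranges tried, 0.01 to 0.65 points for CV death, 0.03 to 1.6 for the composite and 0.07 to 2.8 for HF hospitalization. The upper values need high mortality, and nothing in the SAP shows that to be expected. All-cause death and the primary ADR analysis are not affected.

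**What to change.** In Section 10.3.2:

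- Keep Kaplan-Meier for all-cause death.
- For CV death and for the composite, report and plot the Aalen-Johansen cumulative incidence with 95% CI, with non-CV death as the competing event.
- For first HF hospitalization do the same, with any prior death as the competing event.
- State how deaths of unknown cause are classified, since the first two curves depend on it.
- Add a footnote that these figures are not directly comparable with 1-KM figures from other studies.

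If Section 10.2.5 already specifies this, a cross-reference in Section 10.3.2 is enough.

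The cost is a wording change and standard code in SAS 9.4, the version planned in Section 9.1. The death and cause-of-death data are already needed for the all-cause and CV death outcomes. The one drawback is the loss of like-for-like comparison with 1-KM figures elsewhere, which the footnote makes plain.

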10.3.3 Laboratory data

Descriptive statistics of eGFR at each calculated visit will be summarized in the table. Also, change from baseline in eGFR over time by the calculated visit will be displayed.

11. QUALITY CONTROL

All processes are conducted according to GPSP Standard Operating Procedures (SOP) [\(3\)](#). Appropriate records and documents are stored based on the GPSP SOPs and these processes are checked by internal self-check.

